Title: Comparison of Etomidate Plus Propofol, Etomidate Alone on Induction of Anesthesia

NCT03820388

Document Date: March 15, 2017

1) **Protocol Title**

Comparison of Etomidate Plus Propofol vs. Propofol, Etomidate Alone on Induction of Anesthesia, a Pilot Observational Study

Protocol Version Date: 5/2/2017

2) Objectives

The purpose of this study is compare of etomidate plus propofol vs. propofol or etomidate alone during induction of anesthesia.

The specific aims or objectives are testing patient reactions during induction, and in the post anesthesia care unit (PACU).

The hypotheses to be tested: induction with etomidate combined with propofol when compared to induction with propofol or etomidate alone:

1. will provide less pain during injection,

2. less hypotension (compare to propofol), less hypertension (compare to etomidate) and better hemodynamics than propofol or etomidate during induction,

3. Similar postoperative nausea and vomiting (PONV) when compared with propofol and less PONV when compared with etomidate,

4. Similar pain score among all three groups

3) Background

Induction of anesthesia is a critical part of anesthesia practice. Sudden hypotension, hypertension, arrhythmias, and cardiovascular collapse are threatening complications following injection of induction agent in hemodynamically unstable patients. It is desirable to use a safe agent with fewer adverse effects for this purpose.

Both etomidate and propofol are the most commonly used induction agents for general anesthesia (GA) and both propofol and etomidate have their advantages and disadvantages. Propofol has been associated with injection pain, significant hemodynamic change (hypotension) during induction and less PONV. Etomidate has been associated with more stable hemodynamic and less pain during induction, but more myoclonic movements at induction and PONV. However, those findings are still controversial and the published results are still inconsistent.

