Title: Comparison of Etomidate Plus Propofol, Etomidate Alone on Induction of Anesthesia

NCT03820388

Document Date: September 26, 2017

Statistical Analysis

Sample size calculations were based on our pilot study, and we found MAP to be 80.1 (± 10.3) mmHg, 90.3 (± 10.4) mmHg, 91.0 (± 11.6) mmHg in group P, PE and E at induction. Using PASS 15.0 software, a sample size of 20 patients per group would be needed to detect statistically significant differences with the power of 0.9 and the alpha level of 0.05. Considering a possible 20% dropout rate, 25 patients per group were recruited for the study.

Parametric values were expressed as mean (SD), or percentages of the total number of patients (%). Categorical data were analyzed using χ^2 or Fisher's exact test as appropriate. The hemodynamic parameters among the three groups were compared using the general linear model (GLM). We also considered time of evaluation as a within-subject factor, and the intervention state as a between-subject factor. The time groups (interaction terms) were considered group differences among the three groups in their responses over time. We used Mauchly's sphericity test for compound symmetry assumption. Differences in hemodynamic variables between the three groups at different time points were compared by post hoc Bonferroni test. $P < 0.05$ was considered statistically significant. All statistical analyses were performed with SPSS 22.0 (SPSS; Chicago, IL, USA).

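### For the hemodynamic endpoints, single-step Bonferroni between three groups is valid but more conservative than hypothesis 2 needs; Holm, ideally on its two contrasts, recovers some power

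*SAP*

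**What the plan says.** The SAP (Statistical Analysis) fits a general linear model with time as the within-subject factor and group as the between-subject factor. It then states that differences among the three groups in the hemodynamic variables, taken time point by time point, "were compared by post hoc Bonferroni test". A result with P below 0.05 "was considered statistically significant". The size of the Bonferroni family is not given, either for pairs or for time points.

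The same section bases the sample size on "MAP to be 80.1 (± 10.3) mmHg, 90.3 (± 10.4) mmHg, 91.0 (± 11.6) mmHg in group P, PE and E at induction". It states that "a sample size of 20 patients per group would be needed", "with the power of 0.9 and the alpha level of 0.05", and inflates this to 25 for dropout.

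In the protocol (section 2, Objectives) the lead-in to the hypotheses concerns "induction with etomidate combined with propofol when compared to induction with propofol or etomidate alone". Hypothesis 2, on hemodynamics, sets the combination against propofol for hypotension and against etomidate for hypertension. It contains no propofol vs etomidate comparison. Section 6 makes blood pressure and heart rate changes during induction the primary endpoints.

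**The concern.** The Bonferroni step is applied to the primary endpoints. If it covers three pairs, one third of the error rate goes to propofol vs etomidate, which hypothesis 2 does not ask about. Single-step Bonferroni is also never more powerful than Holm at the same familywise error, on the same data. With about 20 evaluable patients per group, the plan gives up some power on a contrast it was set up to test, and a better option costs almost nothing.

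**Working it through.** **Inputs.** MAP at induction from the SAP: propofol (P) 80.1 (SD 10.3), combination (PE) 90.3 (10.4), etomidate (E) 91.0 (11.6) mmHg; 20 evaluable and 25 recruited per group; alpha 0.05. Assumptions: two-sided tests (sidedness is not stated), three pairs in the Bonferroni family, one variable at one time point, and a common SD.

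**1. The SAP's own figure.**
- Pooled variance = (106.09 + 108.16 + 134.56)/3 = 116.27, so SD = 10.78.
- The mean of the three means is 87.13, and the sum of squared deviations is 74.45.
- Noncentrality of the one-way F test at 20 per group = 20 × 74.45/116.27 = 12.81. Power on 2 and 57 df is 0.887, and 21 per group are needed for 0.90. The stated 20 is within one patient.
- Dropout: 20/(1 − 0.2) = 25, as stated.

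The 0.9 therefore fits the overall three-group test and not a corrected pairwise test.

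**2. PE vs P with a fixed threshold.** Standard error = 10.78 × √(2/n); noncentrality = 10.2/SE; noncentral t on 3n − 3 df.
- n = 20: SE = 3.410, noncentrality 2.991. The critical t is 2.467 at 0.05/3 and 2.302 at 0.05/2. Power is 0.699 and 0.753; unadjusted at 0.05 it is 0.837.
- n = 25: SE = 3.050, noncentrality 3.344. The critical t is 2.451 and 2.289. Power is 0.811 and 0.852.
- At n = 20 the observed difference needed for significance is 2.467 × 3.410 = 8.41 mmHg with three pairs and 2.302 × 3.410 = 7.85 mmHg with two.

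**3. Holm.** With k contrasts, the smallest P value is tested at 0.05/k, the next at 0.05/(k − 1), and so on, stopping at the first failure. Power comes from 1,000,000 simulated trials on the SAP means with SD 10.78 and a pooled variance estimate.

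| Method | PE vs P, n = 20 | PE vs P, n = 25 | PE vs E, n = 20 | PE vs E, n = 25 |
|---|---|---|---|---|
| Bonferroni, three pairs | 0.70 | 0.81 | 0.019 | 0.019 |
| Holm, three pairs | 0.74 | 0.84 | 0.039 | 0.045 |
| Holm, two contrasts | 0.76 | 0.85 | 0.044 | 0.048 |

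At 20 per group, Holm alone gains about 4 points for PE vs P, and dropping the third pair from the family adds about 2 more.

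**4. Error control.** With all means equal and 20 per group, the chance of at least one false rejection among the two hypothesised contrasts is 0.031 at 0.05/3 each and 0.046 with Holm on two. Both are below 0.05; the difference is the unused error.

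**The case against.** The strongest reply is that nothing here is wrong. Three-pair Bonferroni controls error among the pairs at a given time point, and this is a self-described pilot. That stands, and it limits the point to efficiency.

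Several stronger readings are tempting, and the documents do not support them:

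- *The third pair has no value.* Protocol section 7 plans to compare the effects of all three groups on blood pressure and heart rate, and section 12 treats the choice between the two single agents as unsettled. A formal propofol vs etomidate test is defensible. On the SAP means it is also the largest difference (10.9 mmHg, power 0.76 at 20 per group under three-pair Bonferroni).
- *All the hypotheses are affected.* The Bonferroni sentence covers hemodynamic variables only. Hypotheses 1 (injection pain) and 3 (PONV) fall outside it. Hypothesis 4 does span all three groups, but it concerns pain score.
- *The fix is worth more than recruiting 25 per group.* One could read the protocol's 20 mmHg and SD 25 as placing one single agent 20 mmHg on each side of the combination. At 20 per group this gives 0.53 with three-pair Bonferroni and 0.66 with Holm on two, against 0.65 for Bonferroni at 25. The protocol does not state that layout, and the SAP means, with combination and etomidate 0.7 mmHg apart, do not resemble it. Even there, Holm on three pairs also gives 0.66. If only propofol differs, Holm on two gives 0.59, which is below 0.65.

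**Conclusion.** The point holds as an efficiency improvement for the hemodynamic endpoints. For combination vs propofol the gain is about 6 points of power at 20 per group (0.70 to 0.76) and about 4 at 25 (0.81 to 0.85), most of it from Holm itself. For combination vs etomidate the choice makes no practical difference at the SAP's own means, and at 20 per group no correction brings combination vs propofol to 0.9, since even the unadjusted test has 0.84.

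This rests on the SAP's means and SDs, two-sided tests, and a family of three pairs within one variable and time point. The family size is inferred. If time points are also counted in the correction, the plan is more conservative than shown here.

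**What to change.** Replace the post hoc Bonferroni sentence in the SAP with three statements:

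1. The confirmatory hemodynamic contrasts are combination vs propofol and combination vs etomidate, Holm-adjusted to a familywise 0.05.
2. Propofol vs etomidate is reported as a difference with a 95% interval. If the sponsor wants it formally tested, use Holm on all three pairs instead (0.74 rather than 0.76 at 20 per group).
3. The 0.05 applies per variable and time point, unless one primary variable and time point is named. The protocol records four hemodynamic variables at seven times, so Holm on the group contrasts alone does not control error across those 28 combinations.

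The cost is a few lines of SAP text, with no new patients or data; Holm needs only the unadjusted pairwise P values. The small downside is that propofol vs etomidate is not formally tested under the two-contrast option. The change should be fixed before the group comparisons are examined.
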